8.2 DATA QUALITY ASSURANCE

A risk-based approach is used for trial quality management. It is initiated by the assessment of critical data and processes for trial subject protection and reliability of the results as well as identification and assessment of associated risks. An Integrated Quality and Risk Management Plan documents the rationale and strategies for risk management during trial conduct including monitoring approaches, vendor management and other processes focusing on areas of greatest risk.

Continuous risk review and assessment may lead to adjustments in trial conduct, trial design or monitoring approaches.

A quality assurance audit/inspection of this trial may be conducted by the sponsor, sponsor's designees, or by IRB / IEC or by regulatory authorities. The quality assurance auditor will have access to all medical records, the investigator's trial-related files and correspondence, and the informed consent documentation of this clinical trial..

8.3 RECORDS

CRFs for individual subjects will be provided by the sponsor. For drug accountability, refer to Section [4.1.8](#).

8.3.1 Source documents

In accordance with regulatory requirements, the investigator should prepare and maintain adequate and accurate source documents and trial records for each trial subject that include all observations and other data pertinent to the investigation. Source data as well as reported data should follow the 'ALCOA principles' and be attributable, legible, contemporaneous, original, and accurate. Changes to the data should be traceable (audit trail).

Data reported on the CRF must be consistent with the source data or the discrepancies must be explained.

Before providing any copy of subjects' source documents to the sponsor, the investigator must ensure that all subject identifiers (e.g., subject's name, initials, address, phone number, and social security number) have properly been removed or redacted to ensure subject confidentiality.

If the subject is not compliant with the protocol, any corrective action (e.g. re-training) must be documented in the subject file.

For the CRF, data must be derived from source documents, for example:

- Subject identification: sex, year of birth (in accordance with local laws and regulations)

Proprietary confidential information © 2021 Boehringer Ingelheim International GmbH or one or more of its affiliated companies

- Subject participation in the trial (substance, trial number, subject number, date subject was informed)
- Dates of subject's visits, including dispensing of trial medication
- Medical history (including trial indication and concomitant diseases, if applicable)
- Medication history
- AEs and outcome events (onset date [mandatory], and end date [if available])
- SAEs (onset date [mandatory], and end date [if available])
- Concomitant therapy (start date, changes)
- Originals or copies of laboratory results and other imaging or testing results, with proper documented medical evaluation (in validated electronic format, if available)
- ECG results (original or copies of printouts)
- Completion of subject's participation in the trial (end date; in case of premature discontinuation, document the reason for it, if known)
- Prior to allocation of a subject to a treatment into a clinical trial, there must be documented evidence in the source data (e.g. medical records) that the trial participant meets all inclusion criteria and does not meet any exclusion criteria. The absence of records (either medical records, verbal documented feedback of the subject or testing conducted specific for a protocol) to support inclusion/exclusion criteria does not make the subject eligible for the clinical trial.

8.3.2 Direct access to source data and documents

The investigator /institution will allow site trial-related monitoring, audits, IRB / IEC review and regulatory inspections. Direct access must be provided to the CRF and all source documents/data, including progress notes, copies of laboratory and medical test results, which must be available at all times for review by the Clinical Research Associate, auditor and regulatory inspector (e.g. FDA). They may review all CRFs and informed consents. The accuracy of the data will be verified by direct comparison with the source documents described in Section [8.3.1](#). The sponsor will also monitor compliance with the protocol and GCP.

8.3.3 Storage period of records

Trial site:

The trial site(s) must retain the source and essential documents (including ISF) according to contract or the local requirements valid at the time of the end of the trial (whatever is longer).

Sponsor:

The sponsor must retain the essential documents according to the sponsor's SOPs.

8.4 EXPEDITED REPORTING OF ADVERSE EVENTS

BI is responsible to fulfil their legal and regulatory reporting obligation in accordance with regulatory requirements.

8.5 STATEMENT OF CONFIDENTIALITY AND SUBJECT PRIVACY

Individual subject data obtained as a result of this trial is considered confidential and disclosure to third parties is prohibited with the exceptions noted in Section [8.7](#).

Data protection and data security measures are implemented for the collection, storage and processing of patient data in accordance with the principles 6 and 12 of the WHO GCP handbook.

Personalised treatment data may be given to the subject's personal physician or to other appropriate medical personnel responsible for the subject's welfare. Data generated at the site as a result of the trial need to be available for inspection on request by the participating physicians, the sponsor's representatives, by the IRB / IEC and the regulatory authorities.

8.5.1 Collection, storage and future use of biological samples and corresponding data

Measures are in place to comply with the applicable rules for the collection, storage and future use of biological samples and clinical data, in particular

- Sample and data usage has to be in accordance with the informed consent
- The BI-internal or external facilities storing biological samples from clinical trial participants are qualified for the storage of biological samples collected in clinical trials.
- An appropriate sample and data management system, incl. audit trail for clinical data and samples to identify and destroy such samples according to ICF is in place
- A fit for the purpose documentation (e.g. biomarker proposal, analysis plan and report) ensures compliant usage
- A fit for purpose approach will be used for assay/equipment validation depending on the intended use of the data

Samples and/or data may be transferred to third parties and other countries as specified in the ICF.

8.6 TRIAL MILESTONES

The **start of the trial** is defined as the date of the enrolment of the first subject in the trial.

The **end of the trial** ('Last Subject Completed') is defined as the 'date of the last visit of the last subject in whole trial'.

Early termination of the trial is defined as the premature termination of the trial for any reason before the end of the trial as specified in this protocol.

Temporary halt of the trial is defined as any unplanned interruption of the trial by the sponsor with the intention to resume it.

Suspension of the trial is defined as an interruption of the trial based on a Health Authority request.

The EC/competent authority in each participating EU member state will be notified about the trial milestones according to the laws of each member state.

Proprietary confidential information © 2021 Boehringer Ingelheim International GmbH or one or more of its affiliated companies

A final report of the clinical trial data will be written only after all subjects have completed the trial in all countries (EU or non-EU), so that all data can be incorporated and considered in the report.

The sponsor will submit to the EU database a summary of the final trial results within one year from the end of a clinical trial as a whole, regardless of the country of the last patient (EU or non-EU).

8.7 ADMINISTRATIVE STRUCTURE OF THE TRIAL

The trial is sponsored by Boehringer Ingelheim.

The trial will be conducted at [REDACTED] [REDACTED] under the supervision of the Principal Investigator. Tasks and responsibilities are defined in a contract. Relevant documentation on the participating (Principal) Investigators (e.g. their curricula vitae) will be filed in the ISF.

BI has appointed a Clinical Trial Leader, responsible for coordinating all required trial activities, in order to

- Manage the trial in accordance with applicable regulations and internal SOPs
- Direct the clinical trial team in the preparation, conduct, and reporting of the trial
- ensure appropriate training and information of local clinical monitors (CML), Clinical Research Associates, and investigators of participating trial sites

The trial medication will be provided by the [REDACTED] [REDACTED] (BI 706321) or will be obtained by the clinical trial site from public pharmacy (itraconazole).

Safety laboratory tests will be performed by the local laboratory of the trial site [REDACTED]

Analyses of BI 706321 [REDACTED] concentrations in plasma will be performed at [REDACTED]

On-site monitoring will be performed by BI or a contract research organisation appointed by BI.

Data management and statistical evaluation will be done by BI or a contract research organisation according to BI SOPs.

Tasks and functions assigned in order to organise, manage, and evaluate the trial are defined according to BI SOPs. A list of responsible persons and relevant local information can be found in the ISF.

10. APPENDICES

Not applicable.

Proprietary confidential information © 2021 Boehringer Ingelheim International GmbH or one or more of its affiliated companies

## **2. LIST OF ABBREVIATIONS**

See Medicine Glossary:

website: [glossary](#)

Term	Definition / description
ALT	Alanine transaminase
ANOVA	Analysis of variance
AST	Aspartate transaminase
AUC 0-tz	Area under the concentration-time curve of the analyte in plasma over the time interval from 0 to the last quantifiable data point
AUC 0-∞	Area under the concentration-time curve of the analyte in plasma over the time interval from 0 extrapolated to infinity
BMI	Body mass index
BP	Blood pressure
CI	Confidence interval
C max	Maximum measured concentration of the analyte in plasma
CSD	Company Standard Displays
CV	Arithmetic coefficient of variation
F/U	Follow Up
gCV	Geometric coefficient of variation
gMean	Geometric mean

Max	Maximum
Min	Minimum
N	Number non-missing observations
P10	10 th percentile
P90	90 th percentile
PKS	Pharmacokinetic parameter analysis set
PR	Pulse rate
Q1	1 st quartile
Q3	3 rd quartile
R	Reference treatment
RAGe	Report Appendix Generator system
REP	Residual Effect Period

Term	Definition / description
RPM	Report Planning Meeting
SD	Standard deviation
SOC	System organ class
T	Test treatment
TS	Treated set
ULN	Upper limit of normal

### **3. INTRODUCTION**

As per ICH E9 (1) the purpose of this document is to provide a more technical and detailed elaboration of the principal features of the analysis described in the protocol, and to include detailed procedures for executing the statistical analysis of the primary and secondary variables and other data.

This Trial Statistical Analysis Plan (TSAP) assumes familiarity with the Clinical Trial Protocol (CTP), including Protocol Amendments. In particular, the TSAP is based on the planned analysis specification as written in CTP Section 7 “Statistical Methods and Determination of Sample Size”. Therefore, TSAP readers may consult the CTP for more background information on the study, e.g., on trial objectives, trial design and population, treatments, definition of measurements and variables, planning of sample size, randomisation.

Study data (including data entered in the RAVE EDC system and external data provided by suppliers) will be stored in a Clinical Data Repository (CDR).

Pharmacokinetic (PK) parameters will be calculated using Phoenix WinNonlin™ software (version 6.3 or higher, [REDACTED]).

The statistical analyses will be performed within the validated working environment CARE, including SAS™ (current Version 9.4, by [REDACTED]), and a number of SAS™-based tools (e.g., macros for the analyses of adverse events (AE) data or laboratory data; Report Appendix Generator system (RAGe) for compilation/formatting of the CTR appendices).

#### **4. CHANGES IN THE PLANNED ANALYSIS OF THE STUDY**

All analyses as planned in the CTP will be performed and are described in more detail in this TSAP.

## **5. ENDPOINTS**

### **5.1 PRIMARY ENDPOINTS**

#### **Section 2.1.2 of the CTP:**

*The following pharmacokinetic parameters will be determined for BI 706321:*

- *AUC0-∞ (area under the concentration-time curve of the analyte in plasma over the time interval from 0 extrapolated to infinity)*
- *Cmax (maximum measured concentration of the analyte in plasma)*

### **5.2 SECONDARY ENDPOINTS**

#### **5.2.1 Key secondary endpoint**

[figure not shown]
This section is not applicable as no key secondary endpoints have been defined in the CTP.

[figure not shown]
#### **5.2.2 Secondary endpoints**

#### **Section 2.1.3 of the CTP:**

*The following pharmacokinetic parameter will be determined for BI 706321:*

- *AUC0-tz (area under the concentration-time curve of the analyte in plasma over the time interval from 0 to the last quantifiable data point)*

## **6. GENERAL ANALYSIS DEFINITIONS**

### **6.1 TREATMENTS**

For basic study information on investigational products and selection of doses, please see CTP Sections 3 and 4.

The study was performed as an open-label, two-treatment, two-period fixed sequence design trial in healthy male subjects in order to compare the test treatment (T) to the reference treatment (R). The treatments were one oral single dose of [REDACTED] BI 706321 administered as tablet formulation together with multiple oral doses of 200 mg itraconazole as oral solution formulation [REDACTED]

[REDACTED] BI 706321 as tablet given alone (R).

In total, it was planned to assign 14 healthy male subjects to the fixed sequence R-T.

There was a washout period of at least 14 days between the administrations of BI 706321.

For details of dosage and formulation see Table 6.1: 1 below:

Table 6.1: 1 Treatments and labels used in the analysis

Treatment	Short label
R BI 706321 [REDACTED] tablet, single dose	BI
T BI 706321 [REDACTED] tablet, single dose + Itraconazole 20 mL solution, 10 mg/mL, multiple dose	BI+ITZ

The following study phases will be defined for the analysis of AEs:

- **Screening**
  - Ranging from 0:00 h on day of informed consent until administration time of BI 706321 alone in treatment period 1.
- **On treatment** (labelled “BI”, “ITZ”, “BI+ITZ”)
  - **BI alone** (“BI”): Ranging from the time of administration of BI 706321 alone in treatment period 1 until 8 days (192 h) thereafter.
  - **Itraconazole alone** (“ITZ”): Ranging from the time of first administration of itraconazole until time of BI 706321 administration in treatment period 2 OR until 8 days (192 h) after the last administration of itraconazole, if subject discontinues treatment prior to administration of BI 706321.
  - **BI + ITZ** (“BI+ITZ”): Ranging from time of BI 706321 administration in treatment period 2 until 8 days (192 h) after the last administration of itraconazole OR 8 days (192 h) after the BI 706321 administration in treatment period 2, whatever occurs later.
- **Follow-up** (labelled “F/U BI”, “F/U ITZ”, “F/U BI+ITZ”)

- **F/U BI:** Ranging from the end of REP of BI 706321 in treatment period 1 until the first administration of itraconazole in period 2 or until trial termination, whatever occurs first.
- **F/U ITZ** - if applicable - (ranging from 8 days after last administration of itraconazole in treatment period 2 until trial termination if subject discontinues treatment prior to BI 706321 drug administration)
- **F/U BI+ITZ** (ranging from the end of REP of BI 706321 or itraconazole (whatever occurs later) in treatment period 2 until trial termination)

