1.2.2 Itraconazole

Absorption of itraconazole solution is fast with maximum plasma concentration being reached within 2.5 h after oral administration in fasting condition. Bioavailability of itraconazole liquid increases by 30% when given under fasting condition compared to administration together with food [R20-2709]. Mean peak plasma concentrations were 547.7 ng/mL after a single dose of 200 mg itraconazole solution (fasting) and 1965 ng/mL after 15 days of daily treatment with 200 mg itraconazole solution (fasting). Pharmacokinetics of itraconazole is non-linear. The half-life of itraconazole after multiple doses of 200 mg once daily with solution formulation was about 40 h [R17-3742].

In the liver, itraconazole is metabolised extensively to more than 30 metabolites [R17-3743]. Its main metabolite, hydroxy-itraconazole, accounts for about twice the concentration of plasma itraconazole at trough. It has been shown *in vitro* that CYP3A4 is mainly responsible for the formation of this metabolite [R20-2709]. FDA classifies itraconazole as strong index inhibitor of CYP3A and as inhibitor of P-glycoprotein (P-gp) [R18-0241]. However, not only itraconazole contributes to the *in vivo* inhibition of CYP3A observed after itraconazole administration but also three of its metabolites (hydroxy-itraconazole, keto-itraconazole, and N desalkyl-itraconazole) [R10-1102].

For a more detailed description of itraconazole, please refer to the German Summary of Product Characteristics (SmPC) for Sempera® Liquid 10 mg/ml [R20-2709].

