1.2.3 Residual Effect Period

The Residual Effect Period (REP, i.e., the period after the last dose with measurable drug levels and/or pharmacodynamic effects still likely to be present) of BI 706321 is assumed to be 8 days, i.e. based on [redacted] terminal $t_{1/2}$ seen in the FIH trial 1425-0001.

When given together with itraconazole (Treatment T), it is expected that plasma exposure of BI 706321 could be increased (albeit within the exposures explored in the clinical trial 1425-0001), and the time of relevant plasma exposure could be prolonged. This might result in a prolonged period in which adverse effects could potentially occur.

For the use of itraconazole in Treatment T, the REP is defined as 8 days after last administration of itraconazole on Day 11 in Period 2.

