1.4.2.4 Potential drug-drug interaction between BI 706321 and itraconazole

It is likely that concomitant administration of BI 706321 with itraconazole leads to an increase of plasma concentrations and terminal half-life of BI 706321. The effect of itraconazole in increasing C_{max} and AUC of other drugs can be as high as 3.4-fold and 11-fold, respectively, as seen with oral midazolam, a sensitive CYP3A4 substrate, when co-administered with oral itraconazole 200 mg/d [[R01-0516](#), [R20-2709](#)].

Proprietary confidential information © 2021 Boehringer Ingelheim International GmbH or one or more of its affiliated companies

Inhibition of P-gp may increase exposure of sensitive P-gp substrates like fexofenadine by factor 3-4 [[R08-1652](#), [P07-13746](#)] and increase digoxin exposure by ~1.7-fold [[R15-3252](#)]. Therefore, a low dose of [REDACTED] BI 706321 has been selected for this trial (see Section [4.1.2](#)) to ensure that BI 706321 plasma concentrations, even in case of a substantial increase when given with itraconazole, [REDACTED] and that were associated with good safety and tolerability (ref. Section [1.2.1](#)).

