3.3.4 Withdrawal of subjects from treatment or assessments

Subjects may discontinue trial treatment or withdraw consent to trial participation as a whole ('withdrawal of consent') with very different implications; please see sections [3.3.4.1](#) and [3.3.4.2](#) below.

If a subject is removed from or withdraws from the trial prior to the first administration of trial medication, the data of this subject will not be entered in the case report form (CRF) and will not be reported in the clinical trial report (CTR). If a subject is removed from or withdraws from the trial after the first administration of trial medication, this will be documented and the reason for discontinuation must be recorded in the CRF; in addition, the data will be included in the CRF and will be reported in the CTR. At the time of discontinuation, a complete end of trial examination will be performed, if possible, and the information will be recorded in the CRF. If the discontinuation occurs before the end of the REP (see Section [1.2.3](#)), the discontinued subject should if possible be questioned for AEs and concomitant therapies at or after the end of the REP in order to ensure collection of AEs and concomitant therapies throughout the REP, if not contrary to any consent withdrawal of the subject.

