3.3.4.1 Discontinuation of trial treatment

An individual subject will discontinue trial treatment if:

1. The subject wants to discontinue trial treatment, without the need to justify the decision
2. The subject has repeatedly shown to be non-compliant with important trial procedures and, in the opinion of both, the investigator and sponsor representative, is not willing or able to adhere to the trial requirements in the future.
3. The subject needs to take concomitant medication that interferes with the investigational medicinal product or other trial treatment
4. The subject can no longer receive trial treatment for medical reasons (such as surgery, adverse events [AEs], or diseases)
5. An AE or clinically significant laboratory change or abnormality occurs that the investigator assesses as warranting discontinuation of treatment. This may include:
 - The subject has an elevation of AST and/or ALT ≥ 3 -fold ULN
 - The subject has a serious adverse reaction or a severe non-serious adverse reaction
6. The subject has an elevation of AST and/or ALT ≥ 3 -fold ULN and an elevation of total bilirubin ≥ 2 -fold ULN (measured in the same blood sample) and/or needs to be followed up according to the DILI checklist provided in the ISF

In addition to these criteria, the investigator may discontinue subjects at any time based on his or her clinical judgment.

Even if the trial treatment is discontinued, the subject remains in the trial and, given his/her agreement, will undergo the procedures for early treatment discontinuation and follow up as outlined in the [Flow Chart](#) and section [6.2.3](#).

Proprietary confidential information © 2021 Boehringer Ingelheim International GmbH or one or more of its affiliated companies

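### Does the SAP cut the combination-treatment adverse event phase short when itraconazole is stopped before Day 11?

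*SAP*

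**What the plan says.** SAP 6.1 sets the on-treatment phase for the combination as "Ranging from time of BI 706321 administration in treatment period 2 until 8 days (192 h) after the last administration of itraconazole", with the alternative end "8 days (192 h) after the BI 706321 administration in treatment period 2, whatever occurs later". The follow-up phase for the combination begins at the same point, the later of the two residual effect periods (REPs). For BI 706321 alone in Period 1 the phase is 192 h.

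Protocol 1.2.3 describes the REP in general as the time after the last dose during which drug levels or effects are still likely. It assumes 8 days for BI 706321. For itraconazole in treatment T, "the REP is defined as 8 days after last administration of itraconazole on Day 11 in Period 2". It also says of treatment T that "the time of relevant plasma exposure could be prolonged. This might result in a prolonged period in which adverse effects could potentially occur".

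Protocol 7.3.4 assigns adverse events by recorded onset, counts them to treatment up to the end of the REP, and leaves the detailed time intervals to the SAP. Under SAP 6.1, on-treatment events go into CTR Section 15.3 and the registry appendix. Follow-up events appear in Section 15.4 and Appendix 16.2.7.

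**The concern.** Read literally, the protocol ties the itraconazole REP to a dose on Day 11, whereas the SAP ties it to whichever dose was actually last. The two agree for a full course and seem to part when a subject receives BI 706321 and then stops itraconazole early. If the Day 1 dose is the last, treatment T gets exactly the 192 h window used for BI 706321 alone. Yet protocol 1.4.2.4 considers it likely that itraconazole "leads to an increase of plasma concentrations and terminal half-life of BI 706321".

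Early stoppers may also be the subjects of most safety interest. Protocol 3.3.4.1 gives as one reason to stop: "An AE or clinically significant laboratory change or abnormality occurs that the investigator assesses as warranting discontinuation of treatment". If the window were wrongly short, late events in these subjects would leave the on-treatment tables. With 14 subjects, one reclassified subject moves a percentage by 1/14 = 7.1 points, more than the 5% threshold for the non-serious event table in SAP 7.8.1. The REP also guides how long a discontinued subject is questioned: under protocol 3.3.4 he "should if possible be questioned for AEs and concomitant therapies at or after the end of the REP".

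**Working it through.** **Inputs.** BI 706321 is given at 0 h. The protocol Flow Chart puts itraconazole at -1 h on Day 1 and at 23, 46, 70, 94, 118, 142, 166, 190, 214 and 238 h on Days 2 to 11. The REP is 8 × 24 = 192 h for both drugs (protocol 1.2.3, SAP 6.1).

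**The SAP rule.** Phase end = max(last itraconazole dose + 192, 0 + 192).

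| Last itraconazole dose | Itraconazole limb (h) | BI 706321 limb (h) | Phase end (h) | Below 430 h by (h) |
|---|---|---|---|---|
| Day 1 (-1 h) | 191 | 192 | 192 | 238 |
| Day 2 (23 h) | 215 | 192 | 215 | 215 |
| Day 3 (46 h) | 238 | 192 | 238 | 192 |
| Day 5 (94 h) | 286 | 192 | 286 | 144 |
| Day 7 (142 h) | 334 | 192 | 334 | 96 |
| Day 10 (214 h) | 406 | 192 | 406 | 24 |
| Day 11 (238 h) | 430 | 192 | 430 | 0 |

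The range of 192 to 430 h is therefore right, and every stopping day has exactly one end.

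**Did the SAP have early stopping in view?** For a full course the itraconazole limb is 430 h against 192 h, so the choice of the later end could never matter. Among subjects who took the Day 1 itraconazole dose, it matters only if none followed. SAP 6.1 also has an itraconazole-alone phase for a subject who stops before BI 706321, and that phase again ends 192 h after the last dose. Anchoring on the actual last dose is thus applied consistently.

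**Does it depart from the protocol?** The protocol's general definition starts the REP at the last dose, and the itraconazole sentence also refers to the last administration. Day 11 is when the schedule places that dose. A Day 11 anchor has no meaning for someone who took no Day 11 dose. On this natural reading the SAP follows the protocol.

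**How much itraconazole is left when the phase ends?** Protocol 1.2.2 states: "The half-life of itraconazole after multiple doses of 200 mg once daily with solution formulation was about 40 h". Assume first-order decline, so the fraction left = 2^(-hours since last dose / 40).

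- Day 1 stop, 48 h after BI 706321: 2^(-49/40) = 43%.
- Day 1 stop, 96 h: 2^(-97/40) = 19%.
- Day 1 stop, SAP phase end at 192 h: 2^(-193/40) = 3.5%.
- Any later stop, or the full course, at the SAP phase end: 2^(-192/40) = 3.6%.
- Day 1 stop under a fixed 430 h end: 431/40 = 10.8 half-lives, 2^(-431/40) = 0.06%.

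The 43% and 19% fall well inside the window. At its end the fraction left is practically the same for every subject, which is what a last-dose rule is meant to achieve. The calculation is illustrative: protocol 1.2.2 calls itraconazole kinetics non-linear, and the 40 h figure is for multiple dosing.

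**Which events move?** An event or enzyme rise that leads to stopping starts before or around the last dose, so by onset it is on treatment. Only a new event starting more than 192 h after both the last itraconazole dose and BI 706321 falls into follow-up.

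**The case for a change.** The strongest argument concerns BI 706321 rather than itraconazole. Its 8-day REP rests on the half-life in the first-in-human trial, without an inhibitor. Protocol 1.2.3 and 1.4.2.4 expect longer exposure with itraconazole, and the Flow Chart samples BI 706321 to 550 h in treatment T against 190 h in R. Still, the protocol gives no separate BI 706321 REP for treatment T, and the SAP's BI 706321 limb keeps the unadjusted 192 h. This description is accurate. It does not show that the window is too short: the half-life behind the 8 days is redacted, the protocol puts no number on the prolongation, and a subject who stops itraconazole early also has less inhibition. Nor do the documents support 430 h as the right length for that subject. A fixed 430 h would add up to 238 h of background events to the on-treatment count.

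The second argument is that uncertainty about the REP could affect whether late events are asked about at all. That question belongs to protocol 3.3.4, which points to protocol 1.2.3 and not to the SAP. It asks for contact at or after the end of the REP, so later contact is allowed, and protocol 5.2.6.2.1 requires collection until the subject's end of trial. What stands is a point of wording: the protocol could have called Day 11 the planned day of the last dose.

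**Conclusion.** The concern does not hold. The SAP states which end applies after an early stop, the protocol assigns that task to the SAP, and the rule matches the protocol's own last-dose definition. The difference from 430 h is real, 24 to 238 h (24/430 = 5.6% to 238/430 = 55.3%), but it follows from the shorter itraconazole course. It is zero if all subjects complete itraconazole. The documents give no rate of early stopping; the allowance of 2 in 14 in protocol 7.7 covers dropouts and non-evaluable subjects of any kind. Events beyond the phase end are displayed under follow-up, and the PK endpoints are untouched.

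The conclusion rests on reading Day 11 as the planned day of the last dose. The itraconazole fractions also assume a 40 h half-life with first-order decline. A fixed window and a last-dose window are both defensible, and choosing the latter is not an error.
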